## **Appendix 2. Health Assessment Questionnaire Disability Index (HAQ-DI)**

The HAQ-DI score is defined as the average of the scores of eight functional categories (dressing and grooming, arising, eating, walking, hygiene, reach, grip, and other activities), usually administered by the patient. Responses in each functional category are collected as 0 (without any difficulty) to 3 (unable to do a task in that area), with or without aids or devices.

The highest score for questions in each category (range 0 to 3) determines the score for the category, unless aids or devices are required. Dependence on equipment or physical assistance increases a lower score (ie, scores of 0 or 1) to the level of 2 to more accurately represent underlying disability. The eight category scores are averaged into an overall HAQ-DI score on a scale from 0 (no disability) to 3 (completely disabled) when 6 or more categories are non-missing. If more than 2 categories are missing, the HAQ-DI score is set to missing. The HAQ-DI can be treated as a continuous measure.

The HAQ-DI score using aids (and/or devices) is computed by taking the maximum score of the questions in each category (range: [0, 3]) and whether or not aids/devices are used (0 or 1):

$$A = \max(\text{dressing \& grooming category questions, } 2 * \text{aids indicator}) + \\ \max(\text{rising category questions, } 2 * \text{aids indicator}) + \\ \max(\text{eating category questions, } 2 * \text{aids indicator}) + \\ \max(\text{walking category questions, } 2 * \text{aids indicator}) + \\ \max(\text{hygiene category questions, } 2 * \text{aids indicator}) + \\ \max(\text{reach category questions, } 2 * \text{aids indicator}) + \\ \max(\text{grip category questions, } 2 * \text{aids indicator}) + \\ \max(\text{usual activities category questions, } 2 * \text{aids indicator})$$

$$\text{HAQ-DI} = A / (\text{total number of categories with at least 6 non-missing})$$

The following table shows the contribution of the 43 questions used to calculate the HAQ-DI:

HAQ-DI Category:	Category questions: At least 6 categories must have scores to compute the HAQ-DI.		HAQ-DI Category Score with Aids/Devices Calculation:
	Category Questions	Aids/Devices Indicators	
Dressing / Grooming	HAQ0101, HAQ0102 (DRESS, HAIR)	HAQ0114, HAQ0119 (DRSG, GROOM)	
Using each question with a scale of 0-3, calculate the category score as the maximum of the category questions.
 
If the Aids/Devices indicator is “No”, no need to adjust the category score.
 
If the Aids/Devices indicator is “Yes” and the category score is <2, then the category score with the Aids/Devices is set to 2.
 
If the Aids/Devices indicator is “Yes” and the category score is ≥2, then the category score with Aids/Devices is the calculated category score without adjustment.
 
For example:            The Dressing/Grooming category score is 2 if subject answered 1 for both questions 1 and 2 and “Yes” for both question 14 and 18.
 
In the HAQ-DI score calculation, questions on other device/aids will not be used.

Arising	HAQ0103, HAQ0104 (STAND, BED)	HAQ0116, HAQ0120 (CHAIR, ARISING)	
Eating	HAQ0105, HAQ0106, HAQ0107 (MEAT, LIFT, MILK)	HAQ0115, HAQ0121 (UTENSIL, EAT)	
Walking	HAQ0108, HAQ0109 (WALK, STEPS)	HAQ0110, HAQ0111, HAQ0112, HAQ0113, HAQ0122 (CANE, WALKER, CRUTCH, WHEEL, WALKING)	
Hygiene	HAQ0123, HAQ0124, HAQ0125 (WASH, BATH, TOILET)	HAQ0134, HAQ0135, HAQ0137, HAQ0139, HAQ0142 (RAISEAT, BATHBAR, BATHSEAT, LONGBATH, HYGIENE)	
Reach	HAQ0126, HAQ0127 (REACH, BEND)	HAQ0138, HAQ0143 (LONGRCH, REACH)	
Grip	HAQ0128, HAQ0129, HAQ0130 (OPENCAR, JAR, FAUCET)	HAQ0136, HAQ0144 (JAROPEN, GRIP)	
Activity	HAQ0131, HAQ0132, HAQ0133 (SHOP, INCAR, CHORES)	HAQ0145 (ERRAND)	

**Handling Missing Data:** If no more than 2 categories have missing category scores, then the HAQ-DI is the mean of the non-missing category scores. Otherwise, the HAQ-DI score is set to missing.

If any of the category questions are missing, but the aids/device indicator is non-missing, the category score can still be computed. However, if all category questions and its aids/device indicators are missing, then the category score is considered missing.

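### SAP Appendix 2: under the HAQ-DI missing-data rule, a category with no difficulty question answered and aids 'No' scores 0 and counts as observed, while the scoring table beside it gives no score

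*SAP*

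**What the plan says.** SAP Appendix 2 scores each of eight categories from 0 (no difficulty) to 3. In the displayed formula, a category's contribution is the maximum of its difficulty questions and 2 × the aids indicator, which is coded 0 or 1.

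Under Handling Missing Data, two sentences decide whether a category has a score. One deals with unanswered questions where aids use was recorded: "If any of the category questions are missing, but the aids/device indicator is non-missing, the category score can still be computed". The other gives the sole condition under which a category has no score: "However, if all category questions and its aids/device indicators are missing, then the category score is considered missing".

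Two further rules act on the total. "If no more than 2 categories have missing category scores, then the HAQ-DI is the mean of the non-missing category scores". Beyond that limit, "If more than 2 categories are missing, the HAQ-DI score is set to missing".

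The table in Appendix 2 gives the scoring in steps. The category score is the maximum of the category questions. It is left alone if the aids indicator is 'No', and raised to 2 if the indicator is 'Yes' and the score is below 2.

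**The concern.** The condition for a missing category requires the questions and the aids indicators to be blank together. A subject who answers none of a category's difficulty questions, but has 'No' recorded for aids, does not meet it. The formula then has only the aids term left, and that term is 0. A non-answer becomes the best possible score. It also uses up one of the places that the six-category minimum is meant to protect.

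HAQ-DI change at Week 24 is tests 2, 3 and 7 of the hierarchy (SAP Section 3.5), and HAQ-DI is one of the five further ACR20 components (SAP Section 6.2.1). A false 0 at Week 24 looks like improvement, and a false 0 at baseline hides improvement. The missing-data analyses in SAP Sections 6.2.4.2 and 6.3.3.2 act on missing values, so they would pass over it. SAP Section 3.6.2 rules out sensitivity analyses for outliers.

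Other SAP scoring rules work differently. Joint counts (Section 6.1.1) and mTSS (Section 6.3.1.1) are prorated over what was assessed.

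**Working it through.** **Inputs**, all from SAP Appendix 2 unless noted: category score = max(questions, 2 × aids indicator), indicator 0 or 1; a category is missing only if all its questions and its aids indicators are missing; HAQ-DI = mean of the scored categories if at least six of eight are scored. The yardsticks are the 0.22 HAQ-DI decrease (SAP Section 6.4) and the 20% component improvement for ACR20 (SAP Section 6.2.1). Blank questions are ignored in the maximum, as they must be if a partly answered category can be computed.

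**The SAP's own example.** Answers 1 and 1 with aids 'Yes': max(1, 1, 2 × 1) = 2, as stated.

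**The two sets of instructions side by side**

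| Questions | Aids | Missing-data rule with formula | Scoring table |
|---|---|---|---|
| 1 and 1 | Yes | 2 | 2 |
| all blank | Yes | 2 × 1 = 2 | no score to raise |
| all blank | No | 2 × 0 = 0 | no score |
| all blank | blank | missing | no score |

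The third row is the problem: one route gives 0, the other gives nothing.

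**Effect on one subject.** Let *m* be the mean of the answered categories and *k* the number of categories with all questions blank and aids 'No'. The missing-data rule gives (8 − *k*)*m*/8. Treating those categories as missing gives *m* when *k* ≤ 2. The difference is *km*/8.

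For *k* = 1:

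| *m* | Rule as written | Mean of answered | Difference |
|---|---|---|---|
| 1.0 | 7 × 1.0/8 = 0.875 | 1.00 | 0.125 |
| 1.5 | 7 × 1.5/8 = 1.3125 | 1.50 | 0.1875 |
| 2.0 | 7 × 2.0/8 = 1.75 | 2.00 | 0.25 |

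Against the 0.22 threshold, 0.1875/0.22 = 85%, and 0.25 exceeds it.

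For *k* = 2 the score falls by 2/8 = 25% at any non-zero *m*. Against an otherwise unchanged baseline, that alone meets the 20% needed for the HAQ-DI component of ACR20. For *k* = 1 the fall is 12.5%, which does not.

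**The six-category minimum**, at *m* = 2.0: with *k* = 3 the rule gives 5 × 2/8 = 1.25, where treating the three as missing leaves five categories and a missing HAQ-DI. With *k* = 8 it gives 0.00 instead of missing.

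**The case against.** The strongest reply is that the SAP nowhere writes 0 for this case. The table takes the maximum of the questions and makes no adjustment for 'No'; with every question blank there is nothing to take a maximum of. The opening text of Appendix 2 likewise has the questions determine the score and aids raise a low one. The first missing-data sentence can also be read as covering only partly answered categories. This stands to the extent that the 0 is derived, not stated, and that the appendix is inconsistent rather than uniformly wrong. It does not remove the problem. The only sentence that says when a category is missing still excludes this case, and the displayed formula still returns 0.

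Three stronger readings are tempting, and the documents do not support them:

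- **The six-category rule is defeated outright, so a blank questionnaire scores 0.** This happens only if unticked aids are stored as 'No', which is an assumption. If they are stored as blank, the categories are missing and the rule works.
- **The Week 24 comparison is biased in favour of filgotinib.** No frequency is given, the trial is double-blind, and false zeros at baseline and Week 24 act in opposite directions. As an illustration only, if 1% of subjects in each arm had one such category at Week 24 with *m* = 1.5, each arm mean would move by 0.01 × 0.1875 ≈ 0.002 and the difference by about zero.
- **An aids entry should never create a score.** With all questions blank and aids 'Yes', the current rule gives 2. That uses recorded dependence, which Appendix 2 deliberately counts as disability. Making it missing is a choice, not a correction.

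**Conclusion.** The missing-data rule and the scoring table in SAP Appendix 2 disagree when all of a category's difficulty questions are blank and aids is 'No'. Followed with the displayed formula, the missing-data rule gives 0 and counts the category as scored. For an affected subject HAQ-DI is lower by one eighth of the mean of the answered categories for each such category, or 0.125 to 0.25 for means of 1.0 to 2.0. The score is too low only if the category's true score is above 0.

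The effect on the trial's comparisons cannot be sized, because neither the frequency nor the storage of unticked aids is documented. The case for changing the text is that a stated rule on a key secondary endpoint and primary-endpoint component turns non-response into the best score where no planned sensitivity analysis would detect it, and that the repair is small.

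**What to change.** In SAP Appendix 2, replace the sentence that defines a missing category with: *A category score is missing if all its difficulty questions are missing and its aids/device indicator is 'No' or missing.* Then apply the six-category rule. Limit the preceding sentence to match, so that a non-missing 'No' cannot by itself make a category computable.

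State two things separately:

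- whether all questions blank with aids 'Yes' stays at 2, as the current rule has it, or is missing;
- whether an unticked aid is stored as 'No' or as blank.

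The cost is a small text change and about one line of derivation code, to be settled before the database is finalized for the Week 24 analysis. The downside is slightly more missing HAQ-DI scores. The MMRM and multiple imputation already handle these for the HAQ-DI endpoint, and SAP Section 6.2.1 already covers a missing HAQ-DI component in ACR20.

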### **Appendix 3. Treatment Satisfaction Questionnaire for Medication (TSQM)**

TSQM scale scores are computed by adding the items loading on each factor. The lowest possible score is subtracted from this composite score and divided by the greatest possible score minus the lowest possible score. This provides a transformed score between 0 and 1 that should be multiplied by 100. Note that only one item may be missing from each scale before the subscale should be considered invalid for that respondent.

#### **EFFECTIVENESS:**

$([\text{Sum}(\text{Item 1} + \text{Item 2} + \text{Item 3}) - 3] \text{ divided by } 18) * 100$

***If one item is missing***

$([\text{Sum}(\text{Item 1?} + \text{Item 2?} + \text{Item 3?}) - 2] \text{ divided by } 12) * 100$

#### **SIDE-EFFECTS:**

If Question 4 is answered 'No', then score = 100

Else,

$([\text{Sum}(\text{Item 5 to Item 8}) - 4] \text{ divided by } 16) * 100$

***If one item is missing***

$([\text{Sum}(\text{Item 5? to Item 8?}) - 3] \text{ divided by } 12) * 100$

#### **CONVENIENCE:**

$([\text{Sum}(\text{Item 9 to Item 11}) - 3] \text{ divided by } 18) * 100$

***If one item is missing***

$([\text{Sum}(\text{Item 9? to Item 11?}) - 2] \text{ divided by } 12) * 100$

#### **GLOBAL SATISFACTION:**

$([\text{Sum}(\text{Item 12 to Item 14}) - 3] \text{ divided by } 14) * 100$

***If either Item 12 or 13 is missing***

$([\text{Sum}(\text{Item 12? to Item 14?}) - 2] \text{ divided by } 10) * 100$

***If Item 14 is missing***

$([\text{Sum}(\text{Item 12 and Item 13}) - 2] \text{ divided by } 8) * 100$

## Appendix 4. Modified Total Sharp Score

### Modified Sharp Method

The joint erosion score is a summary of erosion severity in 32 joints of the hands and 12 joints in the feet, as shown below for the joints assessed for erosions.

Hands/Fingers MCP: Metacarpophalangeal joints I - V (n = 10)	Hands/Wrist: Multangular bones(trapezium & trapezoid) (n = 2)
Hands/Fingers PIP: Proximal interphalangeal joints II - V (n = 8)	Hands/Wrist: Scaphoid(Navicular) bones (n = 2)
Hands/Fingers IP (thumbs): Interphalangeal joints (n = 2)	Hands/Wrist: Lunate bones (n=2)
Hands/Fingers (thumbs): Proximal Metacarpal joints (n = 2)	Feet/Toes MTP: Metatarsophalangeal joints I – V (n = 10)
Hands/Wrist: Distal Radius (n = 2)	Feet/Toes IP (big toes): Interphalangeal joints (n = 2)
Hands/Wrist: Distal Ulna (n = 2)	

An erosion score of 0 to 5 is given to each joint in the hands and wrists, and a score of 0 to 10 is given to each joint in the feet. Each hand and wrist joint is scored, according to the surface area involved, from 0 to 5, with 5 indicating extensive loss of bone from more than one half of the articulating bone (0 indicates no erosion). Because each side of a foot joint is graded on this scale, the maximum erosion score for a foot joint is 10. Thus, the maximum erosion score for hands and wrists is  $32*5 + 12*10 = 280$ . A joint may not be evaluable due to surgery (i.e., joint replacement) or may be radiographically insufficient for reading.

The joint space narrowing (JSN) score summarizes the severity of JSN in 30 joints of the hands/wrists and 12 joints of the feet, as shown below for the joints assessed for JSN.

Hand/Fingers MCP: Metacarpophalangeal joints I – V (n = 10)	Hand/Wrist: Capitate-scaphoid Joint (n = 2)
Hand/Fingers PIP: Proximal interphalangeal joints II - V (n = 8)	Hand/Wrist: Scaphoid-radius Joint (n=2)
Hand/Fingers CMC: Carpometacarpal joints III, IV, V (n = 6)	Foot/Toes MTP: Metatarsophalangeal joints (n = 10)
Hand/Wrist: Scaphoid-Trapezium Joint (n = 2)	Foot/Toes IP: Interphalangeal joints (n = 2)

Assessment of JSN for each hand (15 joints per hand) and foot (6 joints per foot), including subluxation, is scored from 0 to 4, with 0 indicating no/normal JSN and 4 indicating complete loss of joint space, bony ankylosis, or luxation. Thus, the maximal JSN score is  $(30*4) + (12*4) = 168$ . A joint may not be evaluable due to subluxation, luxations, surgery (i.e., joint replacement) or may be radiographically insufficient for reading.

The mTSS is defined as the erosion score plus the JSN score, with a range of 0 to 448.

The maximum scores (adding up both hands/wrists and feet) are:

Radiography	Maximum score of hands/wrists	Maximum score of feet	Maximum score (add up hands/wrists and feet)
ES (erosion score)	32 joints * 5 score = 160	12 joints * 10 score = 120	280
JSN (joint space narrowing) score	30 joints * 4 score = 120	12 joints * 4 score = 48	168
TSS (Total Sharp score)	280	168	448

**Appendix 5. Corticosteroids**

The following table will be used for converting non-prednisone medications to prednisone equivalent:

*Example: Patient is taking 8 mg of Methylprednisolone orally daily. To get the equivalent dose of prednisone: 8 mg Methylprednisolone = (5\*8)/ 4 = 10 mg prednisone.*

Corticosteroids Name	Equivalent Dose (mg) to 5 mg Prednisone
Betamethasone	0.75
Betamethasone Dipropionate	0.75
Betamethasone Sodium Phosphate	0.75
Cortisone	20
Dexamethasone	0.75
Dexamethasone Palmitate	0.75
Dexamethasone Phosphate	0.75
Dexamethasone Sodium Phosphate	0.75
Hydrocortisone	20
Meprednisone	4
Methylprednisolone	4
Methylprednisolone Acetate	4
Methylprednisolone Sodium Succinate	4
Prednisone	5
Prednisolone	5
Prednisolone Farnesylate	5
Prednisolone Sodium Succinate	5
Triamcinolone	4

## Appendix 6. SAS Programming for Tipping Point Analysis for Binary Endpoint

The following **%tp\_binary** macro generates multiple imputed data and a set of the shift parameters that adjust the imputed values will be examined.

```

/*-----*/
/*--- Delta-Adjustment Method for Tipping Point Analysis for Binary Endpoint ---*/
/*---
/*--- Generate imputed data set for specified shift parameters ---*/
/*--- data= input data set ---*/
/*--- smin= min shift parameter for active drug ---*/
/*--- smax= max shift parameter for active drug ---*/
/*--- sinc= increment of the shift parameter for active drug ---*/
/*--- pmin= min shift parameter for placebo drug ---*/
/*--- pmax= max shift parameter for placebo drug ---*/
/*--- pinc= increment of the shift parameter for placebo drug ---*/
/*--- trt= treatment group indicator ---*/
/*--- out= output imputed data set ---*/
/*-----*/

%macro tp_binary( data=, smin=, smax=, sinc=, pmin=, pmax=, pinc=, trt=, out=);
  data &out;
  set _null_ ;
  run;

  %let ncase_pbo = %sysevalf( (&pmax-&pmin)/&pinc, ceil );

  %do pc=0 %to &ncase_pbo;

    %let pj= %sysevalf( &pmin + &pc * &pinc);

    /*----- # of shift values -----*/
    %let ncase= %sysevalf( (&smax-&smin)/&sinc, ceil );

    /*----- Imputed data for each shift -----*/
    %do jc=0 %to &ncase;

      %let sj= %sysevalf( &smin + &jc * &sinc);

      proc mi data=&data seed=14823 nimpute=20 out=outmi;
        var trt01pn strat1V strat2V strat3V das28n;
        class trt01pn strat1V strat2V strat3V das28n;
        monotone logistic (das28n / link=glogit);
        mnar adjust( das28n(event='1') / adjustobs=(trt01pn="&trt") shift= &sj)
          adjust( das28n(event='1') / adjustobs=(trt01pn='3') shift= &pj);

      run;

      data outmi;
        set outmi;
        Shift Trt= &sj;
        Shift_Pbo= &pj;

      run;

```

```
data &out;  
    set &out outmi;  
run;  
%end;  
%end;  
%mend tp_binary;
```

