### **6.2.3. Primary Analysis of the Primary Efficacy Endpoint**

To test for superiority of filgotinib 200 mg in combination with MTX group versus MTX alone group in proportion of subjects who achieve ACR20 at Week 24, a logistic regression analysis with treatment groups and stratification factors in the model will be used. Subjects who do not have sufficient measurements to establish efficacy at Week 24 will be considered as failures (ie, NRI). The p-value from the logistic regression model for testing the superiority of filgotinib 200 mg in combination with MTX as compared to MTX alone will be provided. The 2-sided 95% confidence interval (CI) of the ACR20 response rate at Week 24 based on normal approximation for each treatment group will be provided for each treatment group. In addition, non-stratified ACR20 response rate difference between treatment groups with its 95% CI based on the normal approximation will be provided.

The comparisons of other filgotinib dose groups versus MTX alone group in proportion of subjects achieving ACR20 at Week 24 will also be conducted with the similar logistic regression model with NRI.

The number and percentage of ACR20 nonresponders observed and nonresponders due to missing at Week 24 will be summarized respectively by treatment groups.

For subjects with observed ACR20 outcomes (ie, responders and observed nonresponders) at Week 24, actual values and change from Baseline at Week 24 in individual components, including TJC68, SJC66, SGA, PGA, Subject's Pain Assessment, and hsCRP, will be summarized by using descriptive statistics (sample size, mean, SD, median, Q1, Q3, minimum, and maximum) by treatment groups.

The proportions of subjects achieving ACR20 (using NRI) will be plotted over time by treatment.

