#### **6.2.4.2. Missing Data Imputation Analyses**

To evaluate the impact of missing data on the ACR20 response rate at Week 24, the following missing value imputation methods will be used:

- The analysis specified in Section 6.2.3 will be performed by using OC and LOCF methods as described in Section 6.1.

- Multiple imputation (MI): The MI procedure replaces each missing binary ACR20 value with a set of plausible values that represent the uncertainty about the right value to impute. Multiple imputed datasets will be generated based on logistic regression models. These multiple imputed data sets are then analyzed by using the method for the primary analysis for complete data as specified in Section 6.2.3. The result of each set of imputed data will be combined using Rubin’s rule {Rubin 1987} and provided. The stratification factors will be included in the imputation model as covariates, and all available data at post-baseline visits up to the time point of interest will be included in the longitudinal model.
- Tipping point analysis: To assess the robustness of analysis results under MNAR (missing not at random) assumption, a delta-adjusting pattern-mixture approach for tipping point analysis {Ratitch 2013} will be conducted for the primary efficacy endpoint. The impact from missing data on the comparisons between filgotinib dose groups versus MTX alone group in ACR20 response rate at Week 24 will be evaluated. Specifically, the proposed method will perform a series of analyses with a range of different values of the shift parameter  $\delta$  applied to the imputed datasets at which the conclusion about the statistical significance of the estimated treatment effect is altered. Each  $\delta$  value is classified as either ‘altering the study’s conclusion’ or tips, ‘keeping the study’s conclusion unchanged’. The tipping points that alter the statistical conclusion will be provided. For each  $\delta$  value, multiple imputed datasets will be generated. The same analysis method for the primary analysis for complete data as specified in Section 6.2.3 will be applied when analyzing adjusted data generated under the different  $\delta$  values.

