  - 2) MI: All subjects with baseline measurement will be included. The MI procedure replaces each missing composite DAS28(CRP) value with a set of plausible values that represent the uncertainty about the right value to impute. Baseline value and stratification factors will be included in the imputation model as covariates, and all available data at baseline and all post-baseline visits through the last available visits will be included in the longitudinal model. The multiple imputed datasets will be generated. These multiple imputed data sets are then used to identify subjects with  $\text{DAS28(CRP)} \leq 3.2$  at Week 12, and analyzed by using the analysis method specified in Section 6.3.2 for complete data. The results from each set of imputed data sets will then be combined using Rubin's rule {Rubin 1987}.
  - 3) Tipping point analysis: Similar tipping point method as described in Section 6.2.4.2 will be applied to DAS28(CRP) < 2.6 response rate at Week 24.
- Change from Baseline in SF-36 PCS at Week 24
  - 1) MI: Similar MI procedure used for analyzing the change from Baseline in the HAQ-DI score at Week 24 will be performed.
  - 2) Tipping point analysis: Similar tipping point analysis method used for analyzing the change from Baseline in the HAQ-DI score at Week 24 will be performed.
- Change from Baseline in FACIT-Fatigue at Week 24
  - 1) MI: Similar MI procedure used for analyzing the change from Baseline in the HAQ-DI score at Week 24 will be performed.
  - 2) Tipping point analysis: Similar tipping point analysis method used for analyzing the change from Baseline in the HAQ-DI score at Week 24 will be performed.

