## Appendix 7. SAS Programming for Tipping Point Analysis for Continuous Endpoint

The following %tp\_conti macro generates multiple imputed data sets and a set of the shift parameters that adjust the imputed values will be examined.

```
*****  
/*--- Modified Tipping Point Analysis from Yuan's method ---*/  
/*---  
/*--- Generate imputed data set for specified shift parameters ---*/  
/*--- data= input data set ---*/  
/*--- smin= min shift parameter for active drug ---*/  
/*--- smax= max shift parameter for active drug ---*/  
/*--- sinc= increment of the shift parameter for active drug ---*/  
/*--- pmin= min shift parameter for placebo drug ---*/  
/*--- pmax= max shift parameter for placebo drug ---*/  
/*--- pinc= increment of the shift parameter for placebo drug ---*/  
/*--- trt= treatment group indicator (eg, 1= filgotinib 200 mg) ---*/  
/*--- out= output imputed data set ---*/  
*****
```

```
%macro tp_conti( data=, smin=, smax=, sinc=, pmin=, pmax=, pinc=, trt=, out=);  
  data &out;  
  set _null_ ;  
  run;
```

```
  %let ncase_pbo = %sysevalf( (&pmax-&pmin)/&pinc, ceil );
```

```
  %do pc=0 %to &ncase_pbo;
```

```
    %let pj= %sysevalf( &pmin + &pc * &pinc);
```

```
    /*----- # of shift values -----*/  
    %let ncase= %sysevalf( (&smax-&smin)/&sinc, ceil );
```

```
    /*----- Imputed data for each shift -----*/  
    %do jc=0 %to &ncase;
```

```
      %let sj= %sysevalf( &smin + &jc * &sinc);
```

```
      proc mi data=&data out=all_mono nimpute=15 seed=123;  
        var v_1 v_2 v_3 v_4 v_5 v_6 v_7 v_8 v_9;  
        mcmc chain=multiple impute=monotone;  
      run;
```

```
      proc sort data=all_mono; by _Imputation_ trt01pn; run;
```

```
      proc mi data=all_mono out=outmi seed=465 nimpute=1;  
        by _Imputation_ ;  
        var trt01pn strat1V strat2V strat3V v_1 v_2 v_3 v_4 v_5 v_6 v_7 v_8 v_9;  
        class trt01pn strat1V strat2V strat3V;  
        monotone regression;  
        mnar adjust( v_5 / adjustobs=(trt01pn="&trt") shift=&sj)  
          adjust( v_5 / adjustobs=(trt01pn='3') shift= &pj);
```

```
run;

data outmi;
    set outmi;
    Shift_Trtr= &sj;
    Shift_Pbo= &pj;
run;

data &out;
    set &out outmi;
run;
%end;
%mend tp_conti;
```

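### The printed tipping-point program for binary endpoints ignores each subject's earlier responses, so its zero-shift point is not the SAP's missing-at-random analysis and the tipping shift is hard to interpret

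*SAP*

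**What the plan says.** The primary ACR20 analysis uses non-responder imputation (SAP 6.2.3): "Subjects who do not have sufficient measurements to establish efficacy at Week 24 will be considered as failures (ie, NRI").

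SAP 6.2.4.2 adds two model-based checks. For the MI, besides the stratification factors, "all available data at post-baseline visits up to the time point of interest will be included in the longitudinal model". The next bullet plans "a delta-adjusting pattern-mixture approach for tipping point analysis" and does not name the predictors of its imputation model. SAP 6.3.3.2 carries the method to the second binary endpoint: "Similar tipping point method as described in Section 6.2.4.2 will be applied to DAS28(CRP") < 2.6 at Week 24. The MI for that endpoint imputes the continuous score from baseline, strata and all visits, and then dichotomises.

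Appendix 6 prints one program for binary endpoints. Its variable list is "var trt01pn strat1V strat2V strat3V das28n", and its imputation statement is "monotone logistic (das28n / link=glogit") with no covariate list. It shifts the active arm by one parameter and the comparator by another: "adjust( das28n(event='1') / adjustobs=(trt01pn='3') shift= &pj").

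Appendix 7, for continuous endpoints, uses "var trt01pn strat1V strat2V strat3V v_1 v_2 v_3 v_4 v_5 v_6 v_7 v_8 v_9".

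**The concern.** The on-treatment dataset ends 7 days after the last dose (SAP 3.8.2). A subject who stops study drug early is therefore missing at Week 24 but will usually have assessments from some of Weeks 2, 4, 8, 12, 16 and 20. The printed program discards them. A subject who failed ACR20 at Weeks 12, 16 and 20 gets the same imputed probability as a subject in the same arm and stratum who was responding.

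A tipping shift is read as a distance from missing-at-random. If zero shift is not missing-at-random given the subject's history, the reader cannot say what the distance is measured from. The robustness statements for the primary endpoint and for DAS28(CRP) < 2.6 would rest on it.

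**Working it through.** **1. The plan's own figures.** The documents give no tipping shift, shift range or missing-data rate to reproduce. The planning figures do reproduce. For mTSS, n per arm = 2 × (z₀.₉₇₅ + z₀.₉₀)² × 2.7² / 0.62² ≈ 398.5, so 399 against the stated 400. For ACR20 at 62% versus 78%, power is 99.9% with 400 versus 400 and 98.3% with 200 versus 400, consistent with the stated figure of over 90%. The rates 62% and 78% are used below as planning assumptions.

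**2. What each model can use.** With no covariate list, only variables placed before the outcome can predict it.

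| Analysis | Baseline value | Earlier visits |
|---|---|---|
| ACR20 MI (6.2.4.2) | not named | yes |
| DAS28(CRP) MI (6.3.3.2) | yes | yes |
| Continuous tipping point (Appendix 7) | visit series `v_1` to `v_9` | yes |
| Binary tipping point (Appendix 6) | no | no |

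**3. Within one arm.** Suppose a subject's history predicts 15% response (assumed). The program starts near the arm rate instead:
- filgotinib 200 mg + MTX: logit(0.78) − logit(0.15) = 1.266 + 1.735 = 3.00
- MTX alone: logit(0.62) − logit(0.15) = 0.490 + 1.735 = 2.22 (unrounded inputs)

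The gap in the arm's response rate is missing share × (arm rate − history-based rate). With 10% missing and a history-based rate h of 15% to 50% (assumed):
- filgotinib 200 mg + MTX: 0.10 × (78 − 15) = 6.3 points, down to 0.10 × (78 − 50) = 2.8
- MTX alone: 0.10 × (62 − 15) = 4.7 points, down to 0.10 × (62 − 50) = 1.2

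**4. In the treatment difference.** 6.3 − 4.7 = 1.6 and 2.8 − 1.2 = 1.6. In general, 0.10 × [(78 − h) − (62 − h)] = 0.10 × 16 = 1.6 points whatever h is. This requires the same missing share and the same h in both arms.

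**5. Dropping the equal-h assumption.** Illustration with assumed inputs: 400 per arm, Week 24 rates 72% and 62%, 10% missing per arm, one earlier binary response with the same rate as Week 24 and correlation 0.6 with it. Pattern (a), filgotinib arm:
- Week 24 response given earlier response: 0.72 + 0.6 × 0.28 = 0.888; given earlier non-response: 0.72 − 0.6 × 0.72 = 0.288
- if earlier non-responders are 3 times as likely to be missing, their share of the missing is 0.84 / (0.84 + 0.72) = 0.538
- rate imputed with history: 0.538 × 0.288 + 0.462 × 0.888 = 0.565
- rate imputed from arm only (the completers' rate): (0.72 − 0.10 × 0.565) / 0.90 = 0.737

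| Who is missing | Arm-only rates, filgotinib / MTX | Rates with history | Error in difference (points) | Log-odds distance to tipping: arm-only, with history |
|---|---|---|---|---|
| (a) non-responders 3×, filgotinib only | 0.737 / 0.620 | 0.565 / 0.620 | +1.7 | −2.09, −1.32 |
| (b) non-responders 3×, both arms | 0.737 / 0.638 | 0.565 / 0.459 | −0.1 | −1.31, −1.31 |
| (c) non-responders 3×, MTX only | 0.720 / 0.638 | 0.720 / 0.459 | −1.8 | −0.59, −1.28 |
| (d) random in both arms | 0.720 / 0.620 | 0.720 / 0.620 | 0 | −1.28, −1.28 |

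The error is 0.10 × (filgotinib gap − MTX gap); in (b), 0.10 × (17.2 − 17.9) ≈ −0.1. The last column is the change in the logit of the filgotinib arm's imputed rate at which z falls to 1.96, with MTX unshifted and an approximate Rubin variance for 20 imputations.

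**6. The scale of the shift.** In (a) both models tip at the same imputed rate, 0.258; only the starting point differs. The last column is on the arm-level scale. A program that conditions on history would apply the shift subject by subject, and then about −2.06 is needed to reach 0.258: 0.538 × expit(−0.905 − 2.06) + 0.462 × expit(2.070 − 2.06) = 0.026 + 0.232 = 0.258. Shifts from the two models are therefore not on one scale, whereas imputed rates are.

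**The case against.** A reader might infer that the program starts from an over-optimistic point, so that the tipping analysis flatters filgotinib. The documents do not support that. They give no dropout rate and no pattern of who goes missing. MTX alone is imputed by the same rule, and over-imputing MTX works against filgotinib. Patterns (b) and (c) show no error or the opposite error, and if earlier responders are the ones missing, the arm-only start is too low (0.709 against 0.819 in the 72% arm). Setting the single-arm gaps of 6.3 or 4.7 points against the planned 16-point difference would also mislead, because part of them cancels.

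Three further objections have weight. First, the sentence about using all visits belongs to the MI bullet; the tipping-point bullet names no predictors, and nothing in the SAP commits zero shift to equal the MI. That is so, but a program whose zero point differs from every other missing-at-random analysis in the plan still needs explaining. Second, the code looks like a template: one DAS28 variable, a placebo label, three strata variables where SAP 3.3 lists two factors. No ACR20 call is printed, so its use for ACR20 is inferred from the appendix title and Section 6.2.4.2. Third, a history-based MI and the observed-case, LOCF and per-protocol analyses are planned anyway, so the tipping analysis is not the only check. With 5% missing at 62% versus 78% and 400 per arm, no filgotinib shift tips the result under either model.

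**Conclusion.** The point holds as a mismatch that makes the tipping shift hard to interpret; it does not hold as a bias in a known direction. Run as printed, Appendix 6 imputes from arm and strata only, so its zero-shift point is not missing-at-random given history, unlike the two MI analyses and the continuous macro.

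The effect on the treatment difference is about 1.6 points at the planned rates, if 10% are missing in both arms and the history-based response is equal; in the illustration it runs from +1.7 to −1.8 points. The missing share, the correlation and the missingness patterns are all assumptions. The primary NRI result is untouched. At stake is the reading of the sensitivity analysis for the primary endpoint and one key secondary endpoint. It should be corrected before the analysis is run.

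**What to change.** - **ACR20:** fill intermittent gaps by arm, place the responses at Weeks 2 to 20 before the Week 24 variable in the imputation, and shift Week 24 only. State that zero shift should agree with the Section 6.2.4.2 MI within simulation error.
- **DAS28(CRP) < 2.6:** include baseline DAS28(CRP) and the earlier visits, or impute the continuous score, shift it and dichotomise. Compare zero shift with the MI in 6.3.3.2, not with 6.2.4.2, which covers ACR20 only. The dichotomising step in 6.3.3.2 names a cut-off of 3.2 at Week 12 and must first be aligned with the endpoint. A binary logistic model need not match that MI closely, because the MI imputes the score itself.
- **Both:** report the imputed response rate in each arm at the tipping point alongside the shift.
- **While editing:** confirm the arm coding (code 3 is labelled placebo) and the strata variables, and print the ACR20 call.

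Cost: somewhat more code and a few sentences in the SAP, with no new data. Early-visit responses may be sparse, and SAP 6.5 already reports low enrolment in some stratum combinations, so the model may need fewer visits or a penalised (bias-reduced) logistic fit.
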